11.8. Pharmacokinetic Endpoints

PK variables measured in plasma include: IRL790 parent drug and two of its metabolites (IRL902 (n-dealkylated) and IRL872 (acetylated)). In addition, biomarker P-Prolactin is also measured.

Samples obtained pre-dose and 2h post dose (C_{max}) on Day 1 and Day 28 will be summarised as interval data (using number (n), arithmetic mean, standard deviation (SD), minimum and maximum value, geometric mean and coefficient of variation (CV%)). If appropriate these will be presented overall for the IRL790 treated group but also according to IRL dose.

In order to potentially assess the pharmacokinetic relationship between the treatment doses (7.5mg b.i.d. upwards) parent drug and metabolite assays obtained pre-dose and 2h post dose (C_{max}) on Day 1 and Day 28 each will be analysed separately.

This analysis will involve application of a polynomial regression model to fit dose or log(dose) vs drug plasma concentration with subsequent evaluation of the significance of the curve fit. However as this is a maximum tolerated dose (MTD) investigation the number of patients in each group is not known in advance. The analysis is therefore dependent on the resulting group sizes.

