V2, 23 OCT 2017	
Section 6.4 Blinding and Randomisation
 
Patient unblinding is also contained within the IRS system to allow the unblinding of patients for both Safety and Statistical purposes within the protocol via web or phone (per Sponsor outlined request).
 
Amended to:
 
Patient unblinding is also contained within the IRS system to allow the unblinding of patients for both Safety and Statistical purposes within the protocol via web or phone. If emergency unblinding is required this responsibility lies solely with the investigator, unblinding for other Safety and Statistical purposes will be managed
	
Response to GNA dated 18Oct17.
 
Response to GNA dated 18Oct17.

	
per Sponsor outlined request.
 
Inclusion Criteria 8
 
Section 7.3 Visit 1 (Day 1)
 
Addition:
 
- Additional Requirements 
Subjects will be required to avoid exposure to direct sunlight from Visit 1 (day 1) until the follow-up visit (day 28).
	
V1, 20 SEPT 2017	Initial	N/A

PROTOCOL SYNOPSIS

TITLE: A randomised, double-blind, placebo-controlled, Phase IIa study evaluating the efficacy and tolerability of IRL790 in Parkinson's disease dyskinesia.
PROTOCOL NO: IRL790C003
INVESTIGATOR STUDY SITES: This study will be conducted at approximately 15 study sites located in the United Kingdom.
OBJECTIVES: Primary objective: To evaluate the efficacy of IRL790 in Parkinson's disease dyskinesia. Secondary objectives: To evaluate the effects of IRL790 on core symptoms of Parkinson's disease. To evaluate the pharmacokinetics, safety and tolerability of IRL790 in patients with Parkinson's disease dyskinesia.

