- **Primary Outcome Measure**

The primary evaluation endpoint is:

- Change in the Unified Dyskinesia Rating Scale (UDysRS) total score from Baseline (Day 1) to Visit 4.

- **Secondary Outcome Measures**

The secondary evaluation endpoints are:

- Change in Total Objective Score (III, IV) of the UDysRS from Baseline (Day 1) to Visit 4.
- Change in daily “OFF”-time as assessed with patient diaries from run-in to Visit 4.
- Change in Unified Parkinson's Disease Rating Scale (MDS-UPDRS) total score of part III (motor), and sum score of Questions 4.1 and 4.2 (dyskinesia) in part IV from Baseline (Day 1) to Visit 4.

- **Exploratory outcome measures**

Additionally a number of exploratory end points will be assessed. The following items will be assessed:

- Unified Parkinson's Disease Rating Scale (MDS-UPDRS), part I (total score), part II (total score) and part IV (total score) from Baseline (Day 1) to Visit 4.
- Unified Parkinson's Disease Rating Scale (MDS-UPDRS) Question 1.2 (Hallucinations and Psychosis) from Baseline (Day 1) to Visit 4.
- Unified Parkinson's Disease Rating Scale (MDS-UPDRS) Question 1.6 (Features of dopamine dysregulation syndrome) from Baseline (Day 1) to Visit 4.
- Clinician's Global Impression of Change in overall PD symptoms from Baseline (Day 1) to Visit 4.
- Daily “ON”-time with troublesome dyskinesia as assessed with patient diaries from run-in to Visit 4.
- Daily “ON”-time as assessed with patient diaries from run-in to Visit 4.

Safety assessments

- Frequency, seriousness and intensity of Adverse Events (AEs).
- Physical examination.
- Electrocardiogram (ECG) recordings.
- Vital signs (blood pressure, heart rate).
- Safety laboratory measurements.

Pharmacokinetic (PK) assessments

- After multiple doses: morning trough and C_{max}
- Dose proportionality after multiple doses based on morning trough and C_{max}
- P-Prolactin Pharmacokinetics

STATISTICAL METHODS:

A single analysis at the conclusion of the investigation is planned and there will be no interim analyses.

All the efficacy safety (including laboratory safety) and pharmacokinetic data collected will be amalgamated into a single database with datasets constructed according to these categories.

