All data will be described and analysed according to Treatment group (IRL790, Placebo), day of assessment (Screening, Day 1 (Baseline), 7, 14, 21, 28, End of Treatment (Day 28 or last observation in the event of withdrawal), plus Follow-up (if appropriate)). However as this is a maximum tolerated dose (MTD) investigation where appropriate summaries according to Dose group may also be described (7.5mg b.i.d. upwards). Each data summary will be supported by individual patient listings.

Power and Sample Size:

Seventy Four (74) evaluable patients (37 per group) are sufficient to demonstrate an effect size of 0.67 between the active treatment and control (IRL790 vs Placebo) for the UDysRS primary endpoint with 80% power and type 1 error rate 0.05 (two tailed).

Recruitment will continue until sufficient evaluable patients are available.

Demographics and Baseline Characteristics:

All basic information regarding the sample of patients recruited to represent the PD population with dyskinesia will be summarised.

Analysis Sets

Three analysis sets (or patient populations) will be evaluated: The Full Analysis Set (FAS), Per Protocol Set (PPS) and the Safety Set (SS). The FAS is considered of primary importance.

Efficacy assessments

The primary efficacy variable is the UDysRS total score.

The secondary efficacy variables involve a subset of the UDysRS, the MDS-UPDRS rating scales and the daily “off” time as assessed with patient diaries. Similarly, the exploratory efficacy variables comprise a number of other subsections from the MDS-UPDRS and patient diaries.

The Change from baseline (Screening) at Day 28 (Visit 4, Week 4) and End of Treatment (Day 28 (Visit 4, Week 4 or earlier in the event of withdrawal) will be derived, summarised and analysed. The End of Treatment last assessment available is considered the primary time-point of interest and will be analysed as interval type data.

Each endpoint will be analysed using an Analysis Of Covariance (ANCOVA) model to compare the two treatment groups (IRL790 vs Placebo). The model will include Change from baseline as the dependent variable, Treatment group as a fixed factor and Baseline as the covariate term. Actual p-values and 95% confidence intervals for least square mean estimates of the treatment effects and differences from placebo will be presented.

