The CGI (an exploratory efficacy variable) however is categorical data which is ordinal in nature and will be analysed using the Van Elteren hypothesis test.

Pharmacokinetic (PK) assessments

PK variables measured in plasma are: IRL790 parent drug and two of its metabolites (IRL902 (n-dealkylated) and IRL872 (acetylated)). In addition, the biomarker P-Prolactin is also measured.

Samples are obtained pre-dose and 2h post dose (C_{max}) on Day 1 and Day 28 and will be summarised as interval data. If appropriate, these will be presented overall for the IRL790 treated group but also according to IRL dose.

To assess the relationship between the treatment doses (7.5mg b.i.d. upwards) and drug plasma concentration a polynomial regression model to fit dose or log(dose) vs plasma concentration for each variable and sampling time will be used. However, this is dependent on the number of patients in each of the dose groups of this maximum tolerated dose (MTD) investigation.

Safety assessments

Safety evaluations include: Adverse events and Concomitant medications reporting, Complete physical examination, Vital signs, ECG (12 lead) and Clinical safety laboratory tests (clinical chemistry, haematology and coagulation). All will be presented as data summaries. No formal statistical analyses will be performed.

Adverse events (Overall, By seriousness, By severity, By relationship) and Concomitant medications (Overall) recorded throughout the investigation will be reported following classification according to MedDRA (SOC/PT) and WHODD (ATC Level 2.4) dictionaries respectively.

All other safety evaluations are performed at Screening, Day 28 (Visit 4 or at Withdrawal) and Follow-up (5-8 days after Visit 4) and will be summarised accordingly.

Safety laboratory samples assayed at the local hospital will be presented as interval summaries according to Site.

SAFETY

Recruitment:

The DSMB will convene after 20 and 40 patients have completed the Follow-Up visit (with adequate safety assessment data) for a formal safety review.

Note that recruitment will continue throughout the 20 and 40 patient DSMB

Data Safety Monitoring Board

The DSMB will convene under the following circumstances:

- The DSMB must meet once the 20th and 40th patient has completed the Follow-Up visit
- The DSMB must meet as soon as there has been a SUSAR

The DSMB has the right to recommend to the Sponsor that the study be suspended, terminated or lower doses be given, if considered appropriate.

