6.2. Dosage and administration

The IMP (2-4 capsules) will be swallowed together with 200 mL of tap water in the morning and in the afternoon approximately 8 hours apart of each administration day, except for Day 28 when the last dose will be taken in the morning at the clinic visit after trough PK sampling.

Titration Phase

The starting dose of IRL790 will be 7.5 mg (three capsules) b.i.d (Visit 1, Day 1).

Formal dose adjustments can be made at the discretion of the treating physician according to the following:

Visit	Adjustment
Visit 2 (Day 7)	The dose can be increased to 10mg b.i.d., maintained at 7.5mg b.i.d. or decreased to 5mg b.i.d
Visit 3 (Day 14)	The dose can be adjusted to 5 mg, 7.5mg or 10mg b.i.d. (2-4 capsules b.i.d.) Note: Dose de-escalation/re-escalation is permitted at Visit 3 but is only in a 2.5mg (1 capsule) step. ⁹

The reasoning for dose adjustment must be recorded in the CRF.

⁹ i.e. Dose re-escalation from 5mg to 10mg b.i.d. or de-escalation from 10mg to 5mg b.i.d. is *not* permitted

Unscheduled dose de-escalation can be made between Visit 1 and Visit 3 only in the case of intolerance; unscheduled dose escalation is not permitted.

Fixed Dose Phase

The fixed IRL790 dose for the remaining 14 days of treatment will be determined on Day 14 (Visit 3) for each patient.

Unscheduled dose de-escalation can be made between Visit 3 and Visit 4 only in the case of intolerance.

There will be no treatment with IRL790 available after end of study participation.

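### The protocol's dose-concentration regression includes Day 1, when dose does not vary, and excludes 5 mg patients on Day 28; the SAP drops it without recording the change

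*Protocol*

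**What the plan says.** The synopsis includes pharmacokinetics in a secondary objective ("To evaluate the pharmacokinetics, safety and tolerability of IRL790 in patients"). Its PK assessments list "Dose proportionality after multiple doses based on morning trough" and C_max.

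The method appears twice in the protocol. The synopsis says that "a polynomial regression model to fit dose or log(dose) vs plasma concentration for each variable and sampling time will be used", with the doses given as 7.5 mg b.i.d. and above. Section 11.8 aims to "assess the pharmacokinetic relationship between the treatment doses (7.5mg b.i.d. upwards) parent drug and metabolite assays obtained pre-dose and 2h post dose", on Day 1 and Day 28, each analysed separately: "This analysis will involve application of a polynomial regression model to fit dose or log(dose) vs drug plasma concentration". It adds a condition: "The analysis is therefore dependent on the resulting group sizes". The same lower limit appears under Statistical Methods in the synopsis: "where appropriate summaries according to Dose group may also be described (7.5mg b.i.d. upwards").

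The dosing rules differ from that range. Under Protocol 6.2 and 7.3 every patient starts on 7.5 mg b.i.d. on Day 1. At Visit 2, "The dose can be increased to 10mg b.i.d., maintained at 7.5mg b.i.d. or decreased to 5mg b.i.d". Visit 3 again allows 5, 7.5 or 10 mg, and unscheduled reduction for intolerance is permitted throughout.

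SAP 7.4 gives descriptive PK summaries, by dose if appropriate. SAP 7.4.2 adds a Wilcoxon rank-sum test on the 2 h minus pre-dose change, without naming the groups. It contains no regression on dose. SAP 2 says that changes from the protocol are given in Section 8. Section 8 covers the CGI and the MDS-UPDRS endpoints and says nothing about PK.

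**The concern.** The stated dose range and sampling days do not fit the dosing scheme, and the SAP does not resolve this. Followed literally, the Day 1 regressions have no dose variation, and the Day 28 regressions discard the patients titrated down to 5 mg. SAP 4.10 expects such patients: it defines a final-dose group of 5 mg b.i.d. or lower.

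Dose titration is central to this trial. If nothing is changed, the dose-exposure regression either disappears without explanation or is run later with a model and dose set chosen after the data are seen. Only a secondary PK result is at stake, not the efficacy comparison.

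**Working it through.** The documents give no figure for this analysis, so there is none to reproduce. The check has three steps.

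**1. What can be fitted.** There are three analytes (IRL790, IRL902, IRL872) and four sampling times (pre-dose and 2 h on Day 1 and Day 28), so 3 × 4 = 12 regressions. A polynomial of degree k needs at least k + 1 distinct doses.

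- Day 1 (6 regressions): the only dose is 7.5 mg. The design matrix has rank 1, an intercept only, so there is no slope. The pre-dose sample also precedes any drug.
- Day 28, 7.5 mg and above (6 regressions): two levels, rank 2. A straight line can be fitted but no curve. The dose ratio is 10/7.5 = 1.33.
- Day 28, all three scheduled doses: three levels, rank 3. A line or a quadratic can be fitted. The dose ratio is 10/5 = 2.

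**2. What leaving out 5 mg costs on Day 28.** For the slope of log concentration on log dose (1 = proportional), the half-width of the 95% CI is

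t(0.975, N − 2) × √ln(1 + CV²) / √Sxx, where Sxx = Σ(ln dose − mean ln dose)².

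The 37 IRL790 patients come from the sample size sections. The dose split and the between-patient CV are assumptions, because the documents give neither.

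Worked example: split 12/13/12 over 5/7.5/10 mg, CV 50%, so √ln(1.25) = 0.472.

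- With 5 mg: N = 37, Sxx = 2.912, t = 2.030. Half-width = 2.030 × 0.472 / √2.912 = 0.56.
- Without 5 mg: N = 25, Sxx = (13 × 12/25) × (ln 1.333)² = 0.516, t = 2.069. Half-width = 2.069 × 0.472 / √0.516 = 1.36.
- Ratio: (2.069/2.030) × √(2.912/0.516) = 2.42. It does not depend on CV.

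The same formula for other assumed splits:

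| Split 5/7.5/10 mg | With 5 mg, CV 30/50/70% | Without 5 mg, CV 30/50/70% | Ratio |
|---|---|---|---|
| 12/13/12 | 0.35 / 0.56 / 0.75 | 0.85 / 1.36 / 1.82 | 2.42 |
| 10/17/10 | 0.38 / 0.61 / 0.82 | 0.84 / 1.35 / 1.80 | 2.19 |
| 6/12/19 | 0.39 / 0.63 / 0.84 | 0.77 / 1.24 / 1.66 | 1.96 |
| 18/12/7 | 0.36 / 0.57 / 0.77 | 1.02 / 1.65 / 2.20 | 2.87 |
| 2/10/25 (few on 5 mg) | 0.52 / 0.84 / 1.13 | 0.78 / 1.25 / 1.67 | 1.48 |
| 25/10/2 (few on 10 mg) | 0.44 / 0.71 / 0.95 | 1.76 / 2.83 / 3.79 | 3.97 |

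If nobody ends on 5 mg, the exclusion costs nothing.

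**3. Whether the SAP replaces the regression.** The rank-sum test in SAP 7.4.2 names no groups. Protocol 6.4 says that only active-arm samples are assayed, so placebo cannot be the comparator. The two final-dose groups in SAP 4.10 are a possible pair, but the SAP does not say so, and a rank test would not estimate a dose slope. SAP Section 8 has no PK entry.

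**The case against.** A reader might infer that the protocol leaves dose proportionality with no workable analysis. The documents do not support that. The listed assessment is after multiple doses, which means Day 28. A straight line in log dose is a polynomial model, is what a proportionality slope needs, and can be fitted on 7.5 and 10 mg. The Day 1 regressions lie outside that assessment, and an analyst would probably pass over them.

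Protocol 11.8 is also conditional: it speaks of a potential assessment and makes it depend on group sizes. That stands, so the regression was never a firm deliverable. But neither document sets a minimum size, and the SAP does not invoke the condition. Leaving a method out of the SAP is not the same as applying the condition.

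Nor is it right to say that the SAP removes 5 mg patients or all dose-related PK. SAP 4.4 divides summary tables by dose group where applicable, SAP 4.10 keeps a group at 5 mg or lower, and SAP 7.4 allows summaries by dose. What is missing is the regression.

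The practical value is modest. Protocol 1.7 already reports dose-linear kinetics in healthy volunteers over a far wider range, and PK is missing from the secondary objectives in Protocol 2.2 and SAP 3.1.3. Even with 5 mg included, most intervals in the table are wide. This limits the importance of the point but does not remove the inconsistency.

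**Conclusion.** The point holds as a correctable error in a secondary PK analysis. It is worth fixing but not critical. Three facts rest on the text alone: no dose slope exists on Day 1; the Day 28 range omits a dose that the protocol allows; and the SAP drops the regression without listing the change.

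The size rests on assumed dose splits of 37 patients. The slope interval is about 1.5 to 2.9 times as wide without 5 mg in most splits tried, and about 4 times with very few patients on 10 mg. The absolute widths also depend on the assumed CV of 30 to 70%.

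A reader might also infer that titration is known to bias the slope. Dose is set partly by tolerability, so bias is plausible, but the documents give no link between exposure and dose reduction. In simulations with a true slope of 1 and an assumed correlation of −0.3 between assigned dose and a patient's own exposure, the mean slope was 0.56 to 0.73 unadjusted. It was 0.86 to 0.93 after adjustment for the Day 1 2 h concentration. These figures illustrate why the slope should be labelled observational; they do not show a failed analysis.

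The primary endpoint, alpha and power are unaffected.

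**What to change.** - **Protocol synopsis (Statistical Methods and PK assessments) and 11.8:** replace the range starting at 7.5 mg with all doses received, that is 5, 7.5 and 10 mg b.i.d., or lower if de-escalated. Limit the regression to Day 28.
- **SAP 7.4:** for each analyte, regress log trough and log 2 h concentration on log actual dose at sampling. Report the slope with a 95% CI and label it observational. State the minimum group sizes; at least two dose levels with 5 or more patients each is a possible convention. Define the dose used in the PK summaries as the dose at sampling. A version adjusted for log Day 1 2 h concentration is optional.
- **SAP Section 8:** record that this replaces the polynomial regression. If the sponsor does not want the estimate, state there that the regression is dropped and why.

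The cost is text in three protocol places and two SAP sections, plus one table of 3 analytes × 2 times = 6 slopes. The samples are already planned (Protocol 8.2.2.1), and dosing does not change. The limits remain: intervals will be wide, dose is not randomised, and the Day 1 adjustment removes only part of any titration bias and may work less well for trough and metabolites.

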3.2. Rationale for study design and dose selection

The pharmacological effects of IRL790 have been evaluated in a range of preclinical animal models. Integrating the preclinical *in vivo* data and *in vitro* assessments for the main molecular target, the dopamine D3 receptor, indicates that efficacy in patients with PD could be expected at doses below 500 nM in plasma.

The Phase 1b study of IRL790 in advanced Parkinson's disease indicated that efficacy could be achieved at such plasma concentrations with retained tolerability and safety and where the biomarker prolactin, indicating target engagement, was moderately elevated.

Given the variability in tolerability of IRL790 in PD patients, the dosing of IRL790 will continue to be personalised and hence flexible dosing will be explored in this study. A flexible dose titration range of 5-10 mg b.i.d. will allow the physician to titrate an optimal dose for each individual patient, while retaining a large margin of safety. Given the plasma half-life of about 7 hours, sufficient coverage during the waking hours of the day is expected.

To mitigate the risk for intolerability and AEs, the protocol allows for flexible dose titration and involves careful monitoring of the patients' well-being.

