11.1. General Considerations

A single analysis at the conclusion of the investigation is planned and there will be no interim analyses (other than data safety reviews) that may impact on the experiment wide type 1 error rate.

All data will be described and analysed according to Treatment group (IRL790, Placebo), Day of assessment (Screening, Day 1 (Baseline), 7, 14, 21, 28, End of Treatment (Day 28 or last observation in the event of withdrawal), plus Follow-up (if appropriate)). However as this is a maximum tolerated dose (MTD) investigation where appropriate summaries according to dose group may also be described.

All interval (quantitative continuous) data will be presented as means, standard deviation, minimum, maximum, median, lower quartile and upper quartile as well as number of observations for both Actual values and Change from baseline data. All Categorical (qualitative binary, ordinal) data will be presented in contingency tables as frequencies and percentages with the denominator the total number of patients available from the relevant analysis set.

Statistical methods applied will be appropriate to the nature and distribution of the data. A (two-sided¹⁰) significance level of 5% (<0.05) will be implemented throughout and in view to the stage of development of the drug no statistical adjustment for 'multiplicity' of analysis testing performed is planned. Graphical displays will be used to support the findings wherever possible. All will use two-sided 95% confidence intervals to allow estimation of the minimum likely effect size, which will be useful when moving the development programme forward to Phase III.

The null hypothesis assumed throughout is that there is no difference between the Active treatment and the Control for any comparison performed (IRL790 vs Placebo). The alternative hypothesis is that there is in fact a difference and this may be in either direction in favour of active or the control.

All data derivations, manipulations and reporting procedures will use SAS v9.4 in a Windows 10 operating system environment. All data summaries will be supported by data listings with individual patient details.

¹⁰ A two tailed type 1 error rate allows satisfaction of a routinely accepted bilateral alternative hypothesis. Strong evidence would be required to justify that the treatment could not adversely affect outcome.

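### Dose proportionality is a listed PK assessment, but the protocol's curve-fit test asks only whether concentration is unrelated to dose, and the SAP contains no dose regression at all

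*Protocol*

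**What the plan says.** **Protocol, what is to be assessed.** The synopsis, under pharmacokinetic assessments, lists "Dose proportionality after multiple doses based on morning trough" and on the maximum concentration.

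**Protocol, how.** The synopsis statistical methods say that "a polynomial regression model to fit dose or log(dose) vs plasma concentration for each variable and sampling time will be used". Section 11.8 gives the purpose as "In order to potentially assess the pharmacokinetic relationship between the treatment doses (7.5mg b.i.d. upwards", and so on. It applies the regression separately to parent drug and metabolites, and to the pre-dose and 2 h samples on Day 1 and Day 28. It would "fit dose or log(dose) vs drug plasma concentration with subsequent evaluation of the significance of the curve fit". The analysis is made to depend on how many patients end up at each dose. Section 11.1 says that a "significance level of 5% (<0.05) will be implemented throughout". No section gives a proportionality hypothesis, a target slope, a test of zero intercept or an acceptance range.

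**Protocol, doses.** Section 3.2: "A flexible dose titration range of 5-10 mg b.i.d. will allow the physician to titrate" for each patient. Section 6.2 allows 5, 7.5 and 10 mg b.i.d. as the final dose, set by the treating physician with reductions for intolerance. It starts every active patient on 7.5 mg b.i.d.

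**SAP.** Section 7.4 plans descriptive summaries by day and time-point and, if appropriate, by dose. Section 7.4.2 tests the change from pre-dose to 2 h with a Wilcoxon rank sum test. There is no regression on dose. Section 8, the list of departures from the protocol, mentions CGI-C and MDS-UPDRS only.

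**The concern.** Proportionality means that concentration is a constant times dose. The significance of a fitted concentration-dose curve is judged against a different null: that dose makes no difference. A proportional drug violates that null, and so does a drug whose exposure rises faster or slower than dose.

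A significant fit would therefore show only that higher doses give higher concentrations. Protocol Section 1.7 already reports dose-linear kinetics in healthy volunteers, so little is learned. A non-significant fit would reflect small groups, an uneven dose split or high variability. Neither result tells the sponsor whether exposure at the top dose rises out of proportion, which is what the synopsis item asks.

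The SAP does not repair this. A rank test of the within-day change does not bear on proportionality, and the loss of the regression is not recorded.

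**Working it through.** **1. The plan's own figure.** No sample size is stated for the PK analysis. The only one is 37 per group for UDysRS (effect size 0.67, 80% power, two-sided 0.05). The noncentral t gives 80.05% power at 36 per group and 81.1% at 37, so the figure is reproduced. It sets 37 active patients as the working number for PK, before missing samples.

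**2. Inputs.**
- From the documents: 37 active patients; doses 5, 7.5 and 10 mg b.i.d.; two-sided 5% level.
- Not in the documents, so assumed and varied: the split over final doses, and the between-patient CV (log-normal, 30% to 80%).

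**3. The two hypotheses.** Write C = A·D^b, so ln C = a + b·ln D.
- Proportionality: b = 1.
- Null of the curve-fit test: all dose coefficients are zero, that is b = 0.

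With three dose levels a quadratic is saturated. Its overall F test is then a one-way ANOVA on 2 and 37 − 3 = 34 degrees of freedom, identical for dose and log(dose).

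**4. Rejection under exact proportionality.** Simulated as C = exp(b·ln(D/7.5) + σZ), σ² = ln(1 + CV²), 10,000 trials per cell, b = 1:

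| Split 5/7.5/10 mg | CV 30% | 40% | 50% | 60% | 80% |
|---|---|---|---|---|---|
| 12/12/13 | 100% | 96% | 84% | 67% | 42% |
| 25/8/4 | 100% | 93% | 80% | 68% | 49% |
| 6/25/6 | 93% | 70% | 48% | 34% | 21% |
| 4/8/25 | 96% | 72% | 45% | 26% | 11% |
| 2/5/30 | 73% | 36% | 16% | 8% | 3% |
| 0/12/25 | 74% | 48% | 31% | 22% | 12% |

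**5. Does the test separate proportional from non-proportional?** Split 12/12/13, CV 40%:

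| True b | 0 | 0.5 | 1 | 1.5 | 2 |
|---|---|---|---|---|---|
| Curve-fit F test | 5% | 43% | 96% | 100% | 100% |
| Log-log test of b = 1 | 99% | 59% | 5% | 59% | 99% |

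The F test climbs steadily with b and nothing marks b = 1. The quadratic term alone rejects in 3% to 11% of trials for all b with this split. Its highest rate anywhere is 32% (25/8/4, b = 2, CV 30%), where it also rejects in 14% under exact proportionality.

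**6. Precision of the slope.** The median 90% CI half-width for b is 0.28 to 0.53 (12/12/13, CV 30% to 60%) and 0.36 to 0.67 (4/8/25). A 95% interval is wider by t(0.975)/t(0.95) on 35 df = 2.030/1.690 = 1.20, giving about 0.34 to 0.64 and 0.43 to 0.80. For illustration, a 0.80 to 1.25 criterion over a two-fold range requires the 90% CI to lie within 1 + ln 0.80/ln 2 = 0.68 and 1 + ln 1.25/ln 2 = 1.32. At b = 1 that is met in at most 20% of trials (12/12/13, CV 30%) and in 0% to 2% of the other 37-patient scenarios.

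**7. Titration.** The 5% in step 5 assumes that dose is unrelated to a patient's own exposure. Suppose instead that patients with lower dose-adjusted exposure tolerate higher doses. At an assumed correlation of 0.3, the between-patient test of b = 1 falsely rejects in about 24% to 37% of trials, depending on the split; at 0.5, in about 58% to 80%. With 12/12/13 and correlation 0.3, the mean slope falls to 0.73 at CV 30% and 0.50 at CV 60%, although the truth is 1.

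**8. Day 1 and the lower dose.** On Day 1 every active patient is to receive the same dose, so dose is constant and no slope can be fitted. Section 11.8 describes the doses as 7.5 mg b.i.d. upwards, while Sections 3.2 and 6.2 include 5 mg. If only two levels enter, nothing beyond a straight line is estimable.

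**The case against.** The strongest reply is that Section 11.8 never uses the word proportionality. It speaks of possibly assessing a relationship between dose and concentration, and for that purpose a test against no relation is the matching test. Proportionality is one synopsis item, absent from the objectives and endpoints in Section 2 and from the SAP. The regression is conditional, and Section 11 leaves detailed methods to the SAP, which has none. Geometric means by dose, if produced, would allow a descriptive look.

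Much of this stands, and it limits the weight of the point. It does not remove it: the synopsis item is there, and no analysis in either document answers it. Being optional does not make the test suitable when it is run.

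Four stronger readings are tempting and not supported:
- *The test would reject in most trials of a proportional drug.* That depends on the CV and the split, and step 4 spans 3% to 100%.
- *Those rejections are an inflated type 1 error.* They are not. The tested null is false under proportionality, so they are power for a different question.
- *The SAP carries the wrong test.* It carries no dose regression, so there is nothing there to replace.
- *A log-log test of slope 1 would hold its 5% level here.* Step 7 shows that it need not, because dose is titrated.

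A polynomial does have a curvature term, so departure is not undetectable in principle. Step 5 shows that the term is of little practical use over a two-fold range.

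**Conclusion.** The concern holds in a limited form. The synopsis lists dose proportionality. The one protocol analysis that could serve it tests the absence of any relation with dose, and the SAP drops that analysis without recording the change. The wrong-null argument follows from the text and needs no simulation. How often the fit would be significant under exact proportionality cannot be stated from these documents, since it rests on an assumed log-normal CV and final dose split. The titration bias likewise rests on an assumed correlation; its direction follows if patients with lower exposure tolerate higher doses. This is a minor point: it concerns a PK assessment and leaves the primary endpoint untouched.

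**What to change.** - **Protocol 11.8:** replace the curve-fit significance criterion with a power model on Day 28 data, ln(concentration) on ln(dose), for trough and 2 h and for parent and each metabolite. Report the slope with its 95% CI against 1 as descriptive. State that a slope different from 0 is not evidence of proportionality.
- **SAP 7.4.2:** add the same model, and record the change in Section 8.
- **Confounding:** state that final dose follows tolerability, so the between-patient slope may be confounded with individual exposure. For the 2 h sample, also regress each patient's ln(Day 28/Day 1 concentration) on ln(final dose/Day 1 dose). This removes stable between-patient differences, provided that accumulation is unrelated to dose. It is not available for trough, because the Day 1 pre-dose sample precedes any drug.
- **Day 1:** drop the dose regression.
- **Dose range:** reconcile the wording in Section 11.8 with Sections 3.2 and 6.2.

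The cost is wording and a few regressions on samples already planned. The drawback is a wide interval over a two-fold dose range: the result may be that departure from proportionality is not excluded.
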